10.1.2 Study Data Management Plan (DMP)

The Study Data Management Plan (DMP) will describe the methods used to collect, check and process clinical data in detail. It will also clarify the roles and responsibilities for the different functions and personnel involved in the data management process. Further the DMP will also describe the data flow and timelines within the study.

10.1.3 Coding tools and dictionaries

Adverse events and diagnoses from medical history will be classified according to the terminology of Medical Dictionary for Regulatory Activities (MedDRA). Concomitant medications will be classified according to the WHO Drug Dictionary. All coding will be performed by PAREXEL.

11. EVALUATION AND CALCULATION OF VARIABLES BY ASTRAZENECA OR DELEGATE

11.1 Calculation or derivation of safety variables

The closest observation prior to first administration of investigational product will be regarded as baseline.

Change from baseline variables will be calculated as the value minus the value at baseline.

11.1.1 Other significant adverse events (OAE)

During the evaluation of the AE data, an AstraZeneca medically qualified expert will review the list of AEs that were not reported as SAEs and DAE (AEs, which leads to discontinuation of the IP). Based on the expert's judgement, significant adverse events of particular clinical importance may, after consultation with the Global Patient Safety Physician, be considered OAEs and reported as such in the Clinical Study Report. A similar review of laboratory/vital signs/ECG data will be performed for identification of OAEs.

Examples of these are marked haematological and other laboratory abnormalities, and certain events that lead to intervention (other than those already classified as serious), dose reduction or significant additional treatment.

11.2 Calculation or derivation of pharmacokinetic variables

The pharmacokinetic (PK) analyses of the plasma concentration data for dapagliflozin will be performed by PAREXEL. Derivation of PK parameters will be performed using the WinNonlin's standard non-compartmental approach (WinNonLin version 5.01, WinNonLin, Pharsight, Mountain View, CA, USA).

The actual sampling times will be used in the PK parameter calculations. Plasma concentrations below limit of quantification (LOQ) will be excluded from the calculations except at time points prior to $C_{ss, \max}$, where plasma concentrations below LOQ will be taken as zero at clinical study protocol time zero and as missing at all other time points in the calculation.

The secondary objective is to determine the PK parameters for dapagliflozin dosed twice a day versus once a day at steady-state.

The following PK parameters will be determined:

- AUC_{τ} Area under plasma concentration-time curve during a dosing interval [amount• time/volume]
- AUC_{ss} Area under plasma concentration-time curve during any dosing interval at steady state [amount• time/volume]
- $C_{ss, av}$ The average concentration at steady state
- $C_{ss, \max}$ Maximum plasma (peak) drug concentration at steady state [amount/volume]
- $C_{ss, \min}$ Minimum (trough) steady state drug concentration in plasma during dosing interval [amount/volume]
- DF% Degree of fluctuation at steady state.
 $DF(\%) = (C_{ss, \max} - C_{ss, \min})/C_{ss, av} \times 100$
- $t_{ss, \max}$ Time to maximum plasma concentration at steady state [h]

11.3 Calculation or derivation of pharmacodynamic variables

The primary objective of the study is to assess the effect of dapagliflozin on % inhibition of glucose re-absorption when dapagliflozin is administered once a day (10 mg) versus twice a day (5 mg every 12 hours) at steady state (after five days of dosing).

The secondary objectives of the study are to assess the effect of dapagliflozin on 24 hour urine glucose excretion when administered once a day (10 mg) versus twice a day (5 mg every

12 hours) at steady state (after five days of dosing), the exploratory objectives to indirectly determine if dapagliflozin may inhibit the rate of gut glucose absorption by comparing the plasma glucose, insulin, GLP-1 and GIP responses to meals accompanied with or without the administration of dapagliflozin.

Urine will be evaluated for volume, total glucose and creatinine. At the end of each 4-hour interval, the total urine sample of that period will be mixed thoroughly and the total volume will be recorded. One aliquot will then be taken for measurement of glucose and creatinine. The amount of glucose excreted during each interval and the total glucose excretion over 24 hours (calculated as the sum of the amounts from each 4-hour interval) will be reported.

Inhibition of glucose re-absorption

For each subject, the amount of renally filtered glucose on Day 5 is calculated using the product of the glomerular filtration rate and the mean serum glucose concentration over the 0-4 (inclusive), 4-8 (inclusive), 8-12 (inclusive), 12-16 (inclusive), 16-20 (inclusive), and 20-24 (inclusive) hourly timed intervals from study period start. The glomerular filtration rate is estimated based on the MDRD (Modification of diet in renal disease) method with the pre-dose serum creatinine value on Day 5. The primary PD measure of percent inhibition of renal glucose re-absorption over 24 hours will be calculated as "*100x the sum of the amounts of glucose excreted in the urine from each 4-hour interval / the sum of the amounts of glucose renally filtered from each 4-hour interval*". Only those 4-hour intervals contributing data for both amounts will be included in this calculation,

Inhibition of rate of gut glucose absorption

For plasma glucose, insulin, GLP-1 (7-36 amide) and GIP the area under the effect time curve until 180 minutes after each meal (AUE_{0-180}) will be calculated for each subject in each period. The AUE_{0-180} will be calculated using the linear trapezoidal rule.

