Abbreviation or special term	Explanation
AE	Adverse event (see definition in section 6.3.1)
ALP	Alkaline phosphatase
ALT	Alanine aminotransferase
ANOVA	Analysis of variance
AST	Aspartate aminotransferase
$AUC_{ss, (0-24)}$	Area under the plasma concentration versus time curve from time zero to 24 hours at steady state [amount•time/volume]
AUC_{τ}	Area under plasma concentration-time curve during a dosing interval [amount· time/volume]
AUC_{ss}	Area under plasma concentration-time curve during any dosing interval at steady state [amount· time/volume]
AZ	AstraZeneca
BID	Twice a day
BMI	Body Mass Index
BMS	Bristol-Myers Squibb
CK	Creatinine kinase
CRF	Case Report Form (electronic/paper)
CSR	Clinical Study Report
$C_{ss,av}$	The average concentration at steady state
C_{max}	Maximum plasma (peak) drug concentration [amount/volume]
$C_{ss,max}$	Maximum (peak) steady state drug concentration in plasma during dosing interval [amount/volume]
$C_{ss,min}$	Minimum (trough) steady state drug concentration in plasma during dosing interval [amount/volume]
DAE	AEs, which lead to discontinuation of the IP
DF%	Degree of fluctuation at steady state
DMP	Data management plan
DVS	Data verification specification
EC	Ethics Committee, synonymous to Institutional Review Board (IRB) and Independent Ethics Committee (IEC)

Abbreviation or special term	Explanation
ECG	Electrocardiogram
EDTA	Ethylenediaminetetraacetic acid
FE	Fractional excretion
FSH	Follicle stimulation hormone
Fup	Follow-up examination
GCP	Good Clinical Practice
GIP	Glucose-dependent insulintropic polypeptide
GLP-1	Glucagon-like peptide 1
HBsAg	Hepatitis B surface antigen
HIV	Human Immunodeficiency Virus
IATA	International Air Transport Association
ICH	International Conference on Harmonisation
IP	Investigational Product
LIMS	Laboratory Information Management System
LOQ	Limit of Quantification
LSLV	Last Subject Last Visit
max	Maximum
MDRD	Modification of Diet in Renal Disease
MedDRA	Medical Dictionary for Regulatory Activities
min	Minimum
n	Number of subject
OAE	Other Significant Adverse Event (see definition in section 11.1.1)
OD	Once a day
PD	Pharmacodynamic
PI	Principal Investigator
PK	Pharmacokinetic
q12 hour	Every 12 hours
$R_{ac(C_{max})}$	R_{ac} =Accumulation ratio for C_{max}
$R_{ac(AUC)}$	R_{ac} =Accumulation ratio for AUC
$AUE_{(0-180)}$	Area under the effect time curve until 180 minutes
SAE	Serious adverse event (see definition in section 6.3.2).
SAP	Statistical analysis plan

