6.3.6 Physical examination

The timing of individual examinations is indicated in the Study Plan ([Table 1](#)). A complete physical include an assessment of the following: general appearance, skin, head and neck, lymph nodes, thyroid, abdomen, musculoskeletal, cardiovascular, respiratory and neurological systems.

Height will be measured in centimetres and weight in kilograms in underwear. Measurements should be taken without shoes and the same scale used for all measurements. BMI will be calculated from the height and weight.

A medical history will be recorded at the enrolment visit only.

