ECG electrocardiogram, GLP glucagon-like peptide, GIP glucose-dependent insulinotropic polypeptide

^a Beginning of period 1.

^b Beginning of period 2

^c Brief history and physical exam

^d To be performed at end of Visit 4 (follow-up)

^e Vital signs will be obtained the volunteer in a supine position (resting in bed for at least 10 minutes)

^f Height will be assessed only at the enrolment visit (Visit 1)

- ^g Safety labs (blood and urine) will be performed at Visit 1, and upon admission on Day –1 and pre-dose on Day 5, and at Visit 4. **At enrolment and follow-up examination, the subjects should be in fasted state for at least 8 hours, on Day –1 of each period for at least 4 hours. Non-caloric beverages are allowed for the fasting period.**
- ^h Performed at Visit 2 only after all inclusion and exclusion criteria have been satisfied on Day 1.
- ⁱ Required for female healthy volunteers only. Serum pregnancy test will be required at Visit 1, on Day –1 of Visits 2 and 3. Healthy female volunteers must have confirmed negative serum pregnancy test from Day –1 of each treatment period prior to receiving the IP
- ^j AEs will be recorded from first intake of IP in period 1 until follow-up, SAEs will be collected from the time when informed consent is obtained until the end of study (including the follow-up visit).
- ^k Urine samples for volume, glucose concentration, creatinine concentration.

Section of protocol affected:

Section 3.1, Overall study design and flowchart, Table2

Previous table:

Table 2 Study Plan for Each Treatment Period

Visit	Day	Nominal IP protocol time	Blood for PD			Blood for PK		Urine for PD	Other
			Plasma glucose	Plasma creatinine	Insulin, GLP-1, GIP	OD dosing	BID dosing		
	-1	15:30							Check for inclusion and exclusion criteria, drug screen including alcohol.
		Pre-dose				1	1		
	1	00:00	X						Breakfast ^b
		00:15				2	2		
		00:30				3	3		
		01:00				4	4		
		01:30				5	5		
		02:00				6	6		
		03:00				7	7		
		04:00				8	8		
		06:00				9	9		
		08:00				10	10		

Visit	Day	Nominal protocol time	IP	Blood for PD			Blood for PK		Urine for PD	Other
				Plasma glucose	Plasma creatinine	Insulin, GLP-1, GIP	OD dosing	BID dosing		
		12:00	X ^a				11	11		Dinner ^b
		12:15						12		
		12:30						13		
		13:00						14		
		13:30						15		
		14:00						16		
		15:00						17		
		16:00					12	18		
		18:00						19		
		20:00					13	20		
2		24:00	X				14	21		Breakfast ^b
		12:00	X ^a							Dinner ^b
3		Pre-dose					15	22		

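### The primary endpoint sets an absolute amount of urinary glucose over a filtered load built on body-surface-indexed MDRD GFR, with no conversion stated, so percent inhibition is rescaled by BSA/1.73

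*Supplement*

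**What the plan says.** Section 11.3 of the protocol gives the derivation of the primary endpoint.

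- **Numerator:** "100x the sum of the amounts of glucose excreted in the urine from each 4-hour interval". This is an absolute amount, not indexed to body size.
- **Denominator:** the filtered load for each 4-hour interval, taken as the "product of the glomerular filtration rate and the mean serum glucose concentration" and summed over intervals.
- **GFR, from the Day 5 sample:** "The glomerular filtration rate is estimated based on the MDRD (Modification of diet in renal disease) method with the pre-dose serum creatinine value". Serum creatinine is the only measured input named. The section gives no GFR units, MDRD equation or body-surface term.

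Amendment 1 adds a percent inhibition for each interval, built the same way. Amendment 2 leaves Section 11.3 alone.

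For the urine, Section 11.3 says "Urine will be evaluated for volume, total glucose and creatinine". Table 1, footnote k, as revised by Amendment 2, still lists "Urine samples for volume, glucose concentration, creatinine concentration". Amendment 1 removed urine creatinine only from the safety urinalysis list in Section 6.3.5. No derivation or analysis in the protocol or its amendments uses the interval urine creatinine.

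Body size is recorded at enrolment (Section 6.2). Section 6.3.6 adds: "Height will be measured in centimetres and weight in kilograms in underwear".

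The synopsis states that the aim is estimation, not hypothesis testing. Section 12.2.4 reports least squares means and their untransformed difference with 95% confidence intervals.

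**The concern.** The endpoint is meant to be the share of filtered glucose that is not reabsorbed. For that, numerator and denominator must refer to the same person. An MDRD estimate refers to a standard body surface of 1.73 m², while the urine comes from the subject's actual body. Unless the estimate is brought back to the subject's own mL/min, the ratio carries a leftover factor of BSA/1.73.

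In a trial that only tested for a difference, a constant per-subject factor would matter little. Here the deliverables are two regimen means in percent and a difference in percentage points, so an error of scale is an error in the reported result. Amendment 1 also passes the percent inhibition values to the exploratory PK/PD analysis.

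**Working it through.** **1. The plan's own precision figure (Section 12.3).** Inputs: total SD 15.4, intra-subject variance one half of the total, 14 completers.

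- Within-subject SD = √(0.5 × 15.4²) = 10.89
- SE of the difference = 10.89 × √(2/14) = 4.116
- Half-width with t on 12 df = 8.97, which rounds to the stated ±9.0

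The planning figure reproduces.

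**2. The scale factor.** Take MDRD as otherwise accurate, so that MDRD = own GFR × 1.73/BSA. Then

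reported % = 100 × urinary glucose / (MDRD × time × mean glucose) = true % × BSA/1.73.

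Write k = BSA/1.73. The indexing to 1.73 m² is a property of the named method; the documents do not state it.

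**3. Individual range.** Section 4.1 admits BMI 18.5-29.9 kg/m² and sets no height limit. Assumptions: heights 155-195 cm, and Mosteller BSA = √(height in cm × weight in kg / 3600).

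| Height, BMI | Weight (kg) | BSA (m²) | k | True 24.5% reported as |
|---|---|---|---|---|
| 155 cm, 18.5 | 44.4 | 1.38 | 0.80 | 19.6% |
| 165 cm, 24 | 65.3 | 1.73 | 1.00 | 24.5% |
| 180 cm, 24 | 77.8 | 1.97 | 1.14 | 27.9% |
| 195 cm, 29.9 | 113.7 | 2.48 | 1.43 | 35.1% |

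**4. Group level.** Assumptions: male height 178 ± 7 cm, female 165 ± 6.5 cm, BMI uniform over the protocol range (simulated).

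| Share male | Mean k | True mean 24.5% reported as | True 5-point difference reported as |
|---|---|---|---|
| 50% | 1.063 | 26.0% | 5.3 |
| 80% | 1.099 | 26.9% | 5.5 |
| 100% | 1.124 | 27.5% | 5.6 |

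Under the same assumptions, 22% to 30% of subjects have k within 5% of 1.

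**5. Effect on the regimen comparison.** A subject's k is practically the same in both periods. A within-subject difference d is recorded as k × d, so zero stays zero and the sign is kept. In a within-subject OD/BID ratio k cancels.

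**6. Effect on precision.** If the planning SD was on the converted scale, the half-width on the indexed scale is 8.97 × root-mean-square k, with that quantity 1.069 to 1.128: about 9.6 to 10.1. Scaling by mean k alone gives 8.97 × 1.063 = 9.5 to 8.97 × 1.124 = 10.1, so nearly all of the widening is plain rescaling. If the planning study used indexed GFR in the same way, ±9.0 stands. The documents do not say which applies.

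**The case against.** The strongest reply is that Section 11.3 is a summary. It also omits the interval length, without which GFR times concentration is a rate and not an amount, and nobody supposes that the programmer would leave that out. Section 12.2.1 sends analytical detail to an SAP that is not shown, and the conversion may be there. This stands in part: one cannot claim that the trial's values will be wrong. But the protocol did not leave this endpoint open. It writes out the ratio and names the GFR input, and a programmer who follows it obtains indexed values. A missing interval length would show at once in impossible percentages, whereas a missing factor near 1.1 would not show.

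The second reply is the crossover. The factor is common to both periods, and the secondary endpoint, 24-hour urinary glucose, compares the regimens without any GFR. This stands, and it limits the point to levels, the size of a non-zero difference and interval width.

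Three stronger readings are tempting and are not supported:

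- *Every value is wrong by up to 43%.* The extremes need individuals at the corners of an assumed height range; subjects near 1.73 m² are barely affected.
- *The unused urine creatinine is an error.* It is a missed check or an unstated purpose. An entry for "Fractional excretion" in the abbreviation list proves nothing about a dropped analysis.
- *Incomplete collections would go undetected.* Subjects are confined to the unit, interval volumes and creatinine are recorded, and an interval lacking either amount is left out. What is missing is a planned use of the creatinine data.

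**Conclusion.** The point holds as a fault of scale in the written definition of the primary endpoint. Followed literally, Section 11.3 reports the true percentage times BSA/1.73. On the assumed samples the regimen means come out about 6% to 12% too high in relative terms, and a non-zero OD-BID difference is inflated in the same proportion. These sizes rest on assumed heights, sex mix, BMI distribution and BSA formula, and on no conversion being made in the SAP.

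A reader might infer that the OD-BID comparison is biased. The documents do not support that: the within-subject design carries the same factor in both periods, so the factor cannot produce or reverse a difference. The sample size statement is not challenged. The matter still deserves correction before analysis, because the percentages and their difference are the stated estimation targets.

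**What to change.** In Section 11.3, state the MDRD equation and its units, and define filtered glucose per interval as MDRD eGFR × (BSA/1.73) × interval length × mean glucose, with BSA from enrolment height and weight and its formula named. Apply the same definition to the interval-level values added by Amendment 1. The cost is a wording change and a few lines of code; no new data are needed. If the SAP already makes the conversion, a sentence in Section 11.3 saying so is enough.

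Optionally, add a supportive analysis from data already collected: 100 × (urine glucose / urine creatinine) × (serum creatinine / mean plasma glucose) over the same intervals. Urine volume cancels, so it checks the result against incomplete collection, which, unlike body size, can differ between periods. Its downside is some added creatinine-assay noise, so it need not be primary.

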12. STATISTICAL METHODS AND SAMPLE SIZE DETERMINATION BY ASTRAZENECA OR DELEGATE

12.1 Description of analysis sets

12.1.1 Pharmacodynamic analysis set

The PD population is defined as all subjects who receive at least one dose of IP and for whom any post-dose data are available. The PD population will be used for the analysis of all PD variables and the analysis will be done according to actual treatment received, regardless of randomisation.

12.1.2 Pharmacokinetic analysis set

All subjects who have evaluable pharmacokinetic data without any protocol deviations/violations deemed to effect the pharmacokinetics of Dapagliflozin will be included in the summaries and listings of the pharmacokinetic data.

12.1.3 Safety analysis set

The safety population is defined as all subjects who receive at least one dose of IP and for whom any post-dose data are available. The safety population will be used for the analysis of all safety variables and the analysis will be done according to actual treatment received, regardless of randomisation. Post-dose data imply that there was a contact during which an opportunity was given to report any health problems.

12.2 Methods of statistical analyses

12.2.1 General principles

All statistical summaries and analyses will be performed by PAREXEL International GmbH using SAS[®] 9.1.3 (SAS[®] Institute, Cary NC, USA) or the statistical package StatXact[®], version 6. Statistical and analytical procedures will be detailed in a Statistical Analysis Plan (SAP).

12.2.2 Subject characteristics

Continuous variables will be summarised using descriptive statistics (n, mean, standard deviation [SD], min, median, max). Categorical variables will be summarised in frequency tables (frequency and proportion) by treatment.

12.2.3 Pharmacokinetics

$AUC_{ss, (0-24)}$, $C_{ss, max}$ and $C_{ss, min}$ will be analyzed using an analysis of variance (ANOVA) model, with sequence, period and treatment regimen (10 mg dapagliflozin OD x 5 days versus 5 mg dapagliflozin BID x 5 days) as fixed effects and subject within sequence as a random effect. $AUC_{ss, (0-24)}$, $C_{ss, max}$ and $C_{ss, min}$ will be log-transformed prior to analysis. Least squares means and differences in least squares means together with corresponding confidence intervals will be back-transformed to provide estimates of geometric means (with 95% confidence intervals) and the ratio of geometric means (with 90% confidence intervals), following adjustment for other factors in the model.

Graphical presentations will be used as appropriate. Examples may include line graphs showing individual or mean development over time.

12.2.4 Pharmacodynamics

The primary objective of this study is to assess the effect of twice-daily dosing versus once-daily dosing of the same total daily dose of dapagliflozin on percent inhibition of glucose re-absorption. The primary pharmacodynamic endpoint (percent inhibition of renal glucose re-absorption over 24 hours), and the secondary pharmacodynamic endpoint (total urinary glucose excretion over 24 hours) will be analyzed using an ANOVA model, with sequence, period and treatment regimen (10 mg dapagliflozin OD x 5 days versus 5 mg dapagliflozin BID x 5 days) as fixed effects and subject within sequence as a random effect. Estimated least square means and difference between treatments least squares means will be reported with 95% confidence intervals, with adjustment for other factors in the model done.

If there is after inspecting ANOVA model diagnostics convincing evidence that one or more of the model assumptions are not valid, a nonparametric analysis of the treatment regimen differences will also be reported using the Hodges-Lehmann estimator of the median difference together with a corresponding exact 95% confidence interval.

Graphical presentations will be used as appropriate. Examples may include line graphs showing individual or mean development over time.

For plasma glucose, insulin, GLP-1 (7-36 amide) and GIP the area under the effect time curve until 180 minutes after each meal (AUE_{0-180}) will be calculated. Baseline adjusted geometric mean differences between both treatment groups will be estimated by a linear model on the log-transformed AUEs after each meal and retransforming the point estimates and 95% confidence intervals. The linear model will include treatment, sequence, period as fixed effects, subjects nested within sequence as random effect and baseline concentration as continuous covariate. AUEs after each meal will be analyzed in a separate model.

Results of the analysis after dinner will be used to determine if dapagliflozin inhibits the rate of gut glucose absorption by comparing the plasma glucose, insulin, GLP-1 and GIP responses to meals accompanied with (5 mg BID) or without the administration of dapagliflozin (10 mg OD).

